
General Overview:

This within-subjects study will examine the effects of daily repeated use of cannabis on pain and its relationship to abuse liability. Healthy, non-treatment seeking cannabis smokers (N=16, 8M, 8F) will be admitted to the research center on 5- South of NYSPI for a 16-day inpatient stay. On the first full inpatient day, participants will smoke active cannabis (4.91% CBD/2.98% THC). Days 2-8 will comprise the Inactive Phase, in which placebo cannabis (0% CBD/THC) will be administered 3x/day. The next 7 days (Day 9-15) will be the Active Phase, in which active cannabis (4.91% CBD/2.98% THC) will be administered at the same time points (Table 1). Participants will complete subjective effects visual analog scales and a cannabis rating form daily, and will complete the Cold-Pressor Test and Quantitative Sensory Testing-Thermal Temporal Summation on Days 1, 2, 5, 8, 9, 12, and 15 to explore three critical questions regarding cannabis' therapeutic utility for pain (as illustrated in Figure 1): 1) If abruptly switching active cannabis to inactive cannabis increases experimental pain sensitivity, i.e. hyperalgesia (Day 2-8; red bars) relative to baseline and if these effects parallel measures of cannabis withdrawal such as disrupted mood and sleep; 2) If pharmacological tolerance to the analgesic and abuse-related effects of cannabis is reversed following 7 days of abstinence from active-THC cannabis (by administering 0% CBD/THC, inactive cannabis): defined as a) a significant decrease in CPT latencies and QST-TTS response following active cannabis administration on Day 12 or Day 15 compared to Day 9 (Active Phase), and b) a significant decrease in subjective visual analog scale ratings of abuse, i.e. 'Good Drug Effect' following active cannabis administration on Day 12 or Day 15 (Active Phase) compared to Day 9 (Active Phase); 3) If tolerance is present/develops to repeated, daily smoked cannabis (4.91% CBD/2.98% THC) administration on measures of experimental pain and abuse liability (green bar): defined as a significant increase in CPT latencies and QST-TTS response and 'good drug effect' after active cannabis administration when Day 9 of the Active Phase is compared to Day 1.

Provide the hypothesis for this research.

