Aim 1. Determine the effects of abstinence from active cannabis (by use of 0% THC cannabis) on experimental pain. We hypothesize that (a) abrupt abstinence will result in increased CPT and QST-TTS responses, indicative of withdrawal-induced hyperalgesia.

Aim 2. Determine if a) tolerance is present (Day 1) and is reversed following abstinence from active cannabis (Days 2-8); b) tolerance develops to daily smoked active cannabis (4.91% CBD/2.98% THC; Days 9-15) administration on pain and abuse liability measures. We hypothesize that: (a) existing analgesic tolerance will be reversed following abstinence from active cannabis; (b) over the course of the active cannabis phase, tolerance will develop to cannabis' analgesic but not abuse-related effects.

Include pertinent information about the relationship of the proposed research to previous studies and describe the significance of the proposed research. Be brief.

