- 1) The Cold Pressor Test (CPT) is a validated and reliable pain-induction procedure that reflects A-delta nerve fiber activity within the autonomic nervous system and closely mimics clinical chronic pain. CPT has been shown to have excellent reliability and predictive validity for medication-induced analgesia, including cannabinoids. For this task, two temperature- controlled circulating water baths maintain warm (36.5-37.5°C) and cold (3.5-4.5°C) water. Participants immerse their hand into a warm bath for 3 min (to standardize baseline skin temperature), then the cold bath, indicating when they first experience pain and withdrawing when the pain gets uncomfortable. Study staff will record time (in seconds) until participants: 1) report discomfort (pain threshold), and 2) withdraw their hand from the cold water (pain tolerance): 15 min.
- 2) Quantitative Sensory Testing-Thermal Temporal Summation (QST-TTS) uses repetitive fixed frequency and intensity heat stimulation to induce central sensitization of C-fibers in the spinal cord and is regarded as an experimental correlate of the 'wind-up' phenomenon in the dorsal horn. As dorsal horn CB-1 activity has been linked to suppression of 'wind-up' and central sensitization (the mechanism purportedly underlying cannabis' efficacy for neuropathic pain), cannabis use may decrease QST-TTS response, mirroring analgesia on the CPT during active cannabis administration vs. placebo. For this task, a Medoc TSA-II NeuroSensory Analyzer with a 30 x 30 mm Peltier thermode applies tonic noxious heat stimulation to the thenar eminence of the palm: the baseline temperature is 32.0°C, increases at a rate of 1°C/s up to 46.5°C, and remains constant for 120 sec. Total duration: 3 min.
- 3) Cold Pressor Test Visual Analog Scale (CPT-VAS): 11-item questionnaire rating the physiological and subjective effects of the cold water on a 100 mm VAS after the CPT: 15 sec.
- 4) Quantitative Sensory Testing-Thermal Temporal Summation Computerized Visual Analog Scale (CoVAS): Participants rate magnitude of perceived pain on a 100 mm VAS during the QST-TTS: 135 sec.
- 5) Physiological response to pain: Heart rate and blood pressure will be measured throughout pain assessments: 2 min.
- 6) Pain Intensity/Bothersomeness Scale (PIBS): Ratings of CPT and QST pain on a 0-to-10 scale: 0 being 'not painful/bothersome at all' and 10 being 'most painful/bothersome feeling imaginable': 10 sec.

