All data analyses will be based on models using repeated measures analysis of variance (RM-ANOVA) analyzed as a function of cannabis condition (active vs. inactive) and day (Day 1-15), and sets of planned comparisons, calculated with SPSS or SUPERANOVA statistical packages. The planned comparisons, outlined below, are a priori, and designed to test the specific hypothesis for each aim. Tests of differences for all comparisons will be based on F-statistics with degrees of freedom corrected, depending on the observed within-subject correlation of the measures, using the method of Geiser and Greenhouse or Huynh and Feldt. Results will be considered statistically significant at $p < 0.05$, using 2-tailed tests. Distribution of demographic variables (ethnicity, age, sex) will be described in terms of means, standard deviations, proportions, and 95% confidence intervals, where appropriate.

Please list all references.

1. Nahin, R.L., *Estimates of pain prevalence and severity in adults: United States, 2012*. *J Pain*, 2015. **16**(8): p. 769-80.
2. Dowell, D., T.M. Haegerich, and R. Chou, *CDC guideline for prescribing opioids for chronic pain—United States, 2016*. *Jama*, 2016. **315**(15): p. 1624-1645.
3. LeResche, L., K. Saunders, S. Dublin, S. Thielke, J.O. Merrill, S.M. Shortreed, C. Campbell, and M.R. Von Korff, *Sex and age differences in global pain status among patients using opioids long term for chronic noncancer pain*. *Journal of women's health*, 2015. **24**(8): p. 629-635.
4. Wasserman, R.A., C.M. Brummett, J. Goesling, A. Tsodikov, and A.L. Hassett, *Characteristics of chronic pain patients who take opioids and persistently report high pain intensity*. *Regional anesthesia and pain medicine*, 2014. **39**(1): p. 13.
5. Chou, R., J.A. Turner, E.B. Devine, R.N. Hansen, S.D. Sullivan, I. Blazina, T. Dana, C. Bougatsos, and R.A. Deyo, *The effectiveness and risks of long-term opioid therapy for chronic pain: a systematic review for a National Institutes of Health Pathways to Prevention Workshop*. *Annals of internal medicine*, 2015. **162**(4): p. 276-286.
6. Dunn, K.M., K.W. Saunders, C.M. Rutter, C.J. Banta-Green, J.O. Merrill, M.D. Sullivan, C.M. Weisner, M.J. Silverberg, C.I. Campbell, B.M. Psaty, and M. Von Korff, *Opioid prescriptions for chronic pain and overdose: A cohort study*. *Annals of Internal Medicine*, 2010. **152**(2): p. 85-92.
7. Statistics, N.C.f.H., *Mortality Data for 2017*. 2018.

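### The protocol defines reversal of tolerance by a contrast that measures its development, and gives QST-TTS the wrong direction

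*Protocol*

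**What the plan says.** The protocol's General Overview poses three questions and gives working definitions for the second and third.

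- **Question 2** asks whether tolerance is reversed after seven days of inactive cannabis. For pain it is defined as "a significant decrease in CPT latencies and QST-TTS response following active cannabis administration on Day 12 or Day 15 compared to Day 9". For abuse liability it is a fall in 'Good Drug Effect' between the same days.
- **Question 3** asks whether tolerance is present or develops with daily active cannabis. It is defined as "a significant increase in CPT latencies and QST-TTS response and 'good drug effect' after active cannabis administration when Day 9" is compared with Day 1.

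Aim 2, in the hypothesis section, assigns the days differently. Part (a) asks whether "tolerance is present (Day 1) and is reversed following abstinence from active cannabis (Days 2-8"; part (b) places development in Days 9-15. The hypotheses follow that order: "existing analgesic tolerance will be reversed following abstinence from active cannabis; (b) over the course of the active cannabis phase, tolerance will develop" to the analgesic but not the abuse-related effects.

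The Experimental Assessments list fixes the direction of each pain measure. For CPT (item 1), "Study staff will record time (in seconds) until participants" report discomfort and withdraw the hand. For QST-TTS (item 2), "cannabis use may decrease QST-TTS response, mirroring analgesia on the CPT during active cannabis administration vs. placebo". Its rating scale (item 4) is a pain scale: "Participants rate magnitude of perceived pain on a 100 mm VAS during the QST-TTS".

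The protocol's Statistical/Data Analysis Plan states: "The planned comparisons, outlined below, are a priori, and designed to test the specific hypothesis for each aim". No comparison follows. The SAP overview refers to sets of planned comparisons and gives no day pair, outcome or direction.

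**The concern.** There are three faults, and they compound.

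1. **Contrast.** A test of reversal by abstinence needs a day before the abstinence. Question 2 has none. Question 3 has one (Day 1), but it stops at Day 9 and so cannot show tolerance developing over Days 9-15.
2. **Direction.** Restored analgesia should raise CPT latency and lower QST-TTS response, and lost analgesia should do the opposite. Both definitions require the two measures to move together.
3. **No tie-breaker.** No text says whether the General Overview or Aim 2 governs. The General Overview is the only place that turns these questions into day contrasts with directions.

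At stake is which result is reported as reversal and which as development. As the documents stand, opposite Aim 2 conclusions from the same data could each cite the protocol.

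**Working it through.** **Setting the passages side by side**

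| Contrast (after active cannabis) | What it can show | Aim | Label in General Overview |
|---|---|---|---|
| Day 9 vs Day 1 | tolerance present on Day 1 and reversed by Day 9 | 2a | question 3: present/develops |
| Day 12 or 15 vs Day 9 | tolerance developing | 2b | question 2: reversed |

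| Change | CPT latency | QST-TTS response | QST-TTS in General Overview |
|---|---|---|---|
| Analgesia restored (Day 9 vs 1) | up | down | up |
| Analgesia lost (Day 12/15 vs 9) | down | up | down |

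The labels are exchanged, and the QST-TTS direction is inverted in both rows. Aim 1 agrees on QST-TTS, because it reads a raised response as hyperalgesia.

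**Size of the effect on classification**

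The plan states no figure for these rules, so the following is illustration.

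*Inputs.* d = 0.7, r = 0.6 and 20 completers come from the sample-size justification; N = 16 comes from Study Details and the General Overview; the tests are two-sided at 0.05. The planning values were stated for active against inactive conditions, so applying them between active days is an assumption.

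*Single contrast (paired t, noncentral t).* dz = 0.7/√(2 × (1 − 0.6)) = 0.783.
- n = 20: noncentrality 0.783 × √20 = 3.50, critical t 2.093, power 0.913.
- N = 16: noncentrality 3.13, critical t 2.131, power 0.833.
- With d = 0.5 (dz = 0.559): 0.660 and 0.552.
- With 0.7 taken directly as dz: 0.844 and 0.745.

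*Question 2 and question 3 rules on CPT alone* (simulation, correlation 0.6 between days, shared Day 9; for the either-day column both later days shift equally):

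| True state | n | Q2 met, Day 15 only | Q2 met, either day | Q3 met |
|---|---|---|---|---|
| Development only (Day 9 = Day 1) | 20 | 0.91 | 0.97 | 0.025 |
| | 16 | 0.83 | 0.94 | 0.025 |
| Reversal only (no change after Day 9) | 20 | 0.025 | 0.046 | 0.91 |
| | 16 | 0.025 | 0.046 | 0.83 |

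Under reversal only, question 2 is met no more often than when nothing changes (about 0.046 for either day).

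*QST-TTS.* With a true loss of analgesia of the same size, the probability of a significant result in the printed direction is 5.8 × 10⁻⁸ at n = 20 and 4.5 × 10⁻⁷ at N = 16.

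*Both measures required on one contrast, equal effects.* As printed, the rule is met with probability about 0. With the QST-TTS direction corrected it is met with probability 0.83 at n = 20 (0.913² = 0.83, independent measures) to 0.85 (correlation 0.5 between measures), and 0.69 to 0.73 at N = 16. With dz = 0.70 these become 0.71 to 0.74 and 0.55 to 0.61.

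*Either-day clause.* With no true change, accepting a fall on Day 12 or Day 15 raises the chance of a false significant decrease from 0.025 to about 0.046 per measure.

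**The case against.** The best defence is that this is an exchange of labels in a pilot study. Both contrasts that Aim 2 needs appear in the General Overview, and every required day is a pain-testing day. Two-tailed tests will find a difference in either direction. The protocol's analysis section and the SAP both tie the planned comparisons to the aims, so an analyst would naturally follow Aim 2. If the study's own hypothesis is true (reversal by Day 9, then development), the exchanged CPT labels usually agree: in the simulation, the question 2 and question 3 verdicts match in 87-91% of trials at n = 20 and 79-84% at N = 16, and in about 94-96% when nothing changes. Figure 1, which the General Overview cites, is not visible here and might show the intended pairing.

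Much of this stands. Estimates and p-values are unharmed, and on CPT the damage is confined to cases where only one of the two effects is present. Those are the cases the two questions exist to separate. The agreement argument also does not reach QST-TTS, whose direction is wrong whenever there is a real effect. Following Aim 2 would be sensible, but it would be an undocumented choice made at the analysis stage against the only printed definitions. A figure could show intent without changing the printed definitions.

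**Conclusion.** The concern holds and must be fixed. The exchanged contrasts and the inverted QST-TTS direction follow from the documents' own wording and depend on no calculation. How they do harm depends on a reading the documents leave open:

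- **Measures judged separately:** the QST-TTS part fails, and newly developed tolerance on CPT is counted as reversal. A lasting reversal is missed by question 2 and appears only under question 3.
- **Measures judged jointly:** a coherent loss of analgesia essentially cannot satisfy the pain rule.

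The probabilities rest on the borrowed planning values, and the joint figures also on equal effects in both tests. At d = 0.5 the mislabelling on Day 15 alone falls to 0.66 (n = 20) or 0.55 (N = 16), but the direction of the error is the same.

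**What to change.** Amend the General Overview and list the comparisons in the SAP:

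- **Reversal (Aim 2a):** Day 9 vs Day 1 after active cannabis. CPT latency higher, QST-TTS (CoVAS) response lower, 'Good Drug Effect' higher.
- **Development (Aim 2b):** Day 12 and Day 15 vs Day 9. CPT latency lower, QST-TTS response higher. Test 'Good Drug Effect' separately: a fall would indicate tolerance to abuse-related effects, which Aim 2b predicts will not occur.
- State whether CPT and QST-TTS are judged jointly or separately, and whether CPT threshold or CPT tolerance time decides.
- State how Day 12 and Day 15 are combined, with an adjustment if either day may count.
- Define the CPT direction in Aim 1, where an increased CPT response is read as hyperalgesia; that does not fit if response means latency.

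The cost is wording only, with no new data. Because the protocol says the study is already in data analysis, date the amendment, describe it as made after data collection, and state whether results had been seen.

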Facility Director for Main Site

[name]

Email: [contact]

Phone:

Study Details

Describe the purpose of the investigation. If this is a clinical trial, this should include a description of the disease and the goals of the research.

Chronic pain is a significant public health concern in the U.S., for which prescription opioids have historically been the standard treatment. This has resulted in striking rates of opioid use disorders and fatal overdoses. Identifying non-opioid medications for the management of chronic pain with minimal abuse liability is a public health necessity, and cannabinoids are a promising drug class for this purpose. More than 80% of medicinal cannabis users report pain as their primary medical indication. These patients tend to seek products that are low in delta-9-tetrahydrocannabinol (THC; the primary psychoactive, and thus intoxicating, component of cannabis), and high in cannabidiol (CBD), a cannabinoid that purportedly has therapeutic benefit for pain but does not produce intoxicating effects [1]. However, there are few well-controlled human laboratory studies assessing the efficacy of high-CBD cannabis for pain in the context of abuse, and even less is known regarding the effects of daily repeated use of cannabis on pain and its relationship to abuse liability. Carefully controlled research is needed. The proposed randomized, within-subjects, placebo-controlled 16-day crossover inpatient human laboratory pilot study (N = 16 healthy cannabis users; 8 men, 8 women) will address three important gaps in our understanding of the potential therapeutic utility of cannabis for pain: 1) If abruptly switching active cannabis (4.91% CBD/2.98% THC) to inactive cannabis (0% CBD/THC) increases experimental pain sensitivity, i.e. hyperalgesia, relative to baseline and if these effects parallel measures of cannabis withdrawal such as disrupted mood and sleep (Each cigarette contains approximately 39.28mg of CBD and 23.84mg of THC. They smoke 75% of one cigarette, so each dose is approximately 29.46mg of CBD and 17.88mg of THC); 2) If tolerance to the analgesic and abuse-related effects of cannabis is reversed following 7 days of abstinence from active-THC cannabis (by administering 0% CBD/THC, inactive cannabis); 3) If tolerance is present/develops to repeated, daily smoked cannabis (4.91% CBD/2.98% THC) administration on measures of experimental pain and abuse liability. Two distinct modalities of experimental pain will be assessed: The Cold Pressor Test (CPT) and Quantitative Sensory Testing Thermal Temporal Summation (QST-TTS). The study will start with a day of active cannabis administration (4.91% CBD/2.98% THC) given 3x/day in order to standardize cannabis exposure across participants (Day 1), and will be followed by a 7-day "inactive phase" (Day 2-8) in which participants will smoke inactive cannabis (0% CBD/THC) 3x/day during this 7-day period. The last 7 days (Day 9-15) will comprise an "active cannabis phase" in which participants will smoke cannabis (4.91% CBD/2.98% THC) 3x/day. Throughout the study, experimental pain and abuse-related effects will be assessed, as will sleep and subjective mood assessments. With rates of chronic pain increasing and limited availability of safe and effective treatment alternatives to opioids, this study will provide essential data regarding the efficacy of daily cannabis use on measures of analgesia and abuse liability and the consequences of cannabis abstinence on measures of pain, as it is possible that abrupt cessation of cannabis use will lead to worsened baseline pain.

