Since we will recruit moderate-heavy cannabis users with varied use patterns, they will enter the study with varying pharmacological tolerance. Therefore, Study Day 1 will be an initial day of active cannabis administration to standardize exposure to the same strength of smoked cannabis across participants prior to enforced abstinence from active cannabis in the Inactive Phase (Day 2-8). Participants will be administered active cannabis (two one 4.91% CBD/2.98% THC cigarettes) at 1000h, 1300h, and 1600h.

Days 2-8 (Inactive Phase)

On Study Days 2-8, participants will be administered one inactive cannabis cigarette (0.00% CBD/THC) at the same three time-points (1000, 1300, 1600). We have shown that inactive cannabis controls for expectancy effects of smoking, producing small but reliable increases in ratings of 'high' [5]. Therefore, this phase will assess how abstinence from active- THC cannabis affects pain outcomes in parallel to measures of cannabis intoxication and withdrawal (mood, sleep).

Days 9-15 (Active Phase)

On Study Days 9-15 participants will be administered an active cannabis cigarette (one 4.91% CBD/2.98% THC cigarette) at the same three time-points (1000, 1300, 1600), with the exception of Day 15 where they will be administered active cannabis only at 1000. This phase will allow us to see if CPT and QST pain outcomes and abuse liability change over time

Move Out

Following completion of all assessments of Day 15, the PI will discuss with the participants benefits of cannabis cessation, highlighting availability of a range of treatment options, prior to discharge. At 180 minutes post-cannabis administration, participants will complete field sobriety tests, vital signs, and a Mini-Mental State Exam (MMSE), and will be permitted to leave once they meet discharge criteria. Criteria for discharge will be met when participants report no ongoing subjective drug effects and have no signs of impairment or intoxication, pass the field sobriety test, have normal vitals, and a normal mental status score as assessed by the MMSE. [name], [name], or [name] will make the final determination that the patient is sober and medically stable and can leave the facility.

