The effects of smoked cannabis are typically gone within 3 hours. In the rare event that a participant is still impaired at the conclusion of Study Day 15, they will be asked to remain in the laboratory until the effects wear off, and will be paid extra (i.e., \$10 per hour for any additional time they remain in the laboratory). Participants may be sent home in a taxi, for which they will be reimbursed. They will be allowed to leave the facility when they pass the field sobriety test and are medically stable. They will be instructed not to drive a car or use other drugs or alcohol for 8 hours after administration of cannabis; therefore, participants will be required to take public transportation (i.e., bus or subway) from the laboratory on Day 15, for which they will be reimbursed (included in their pay for Day 15).

CPT and QST-TTS

On Days 1, 2, 5, 8, 9, 12, and 15, participants will complete the CPT and QST-TTS pain tasks 30 minutes before the 1000h cannabis administration (baseline), and 0, 15, 30, 45, 60, and 90 minutes post-cannabis administration. Participants will also complete measures of CPT-induced discomfort (CPT-VAS, PIBS) and will continuously rate the magnitude of perceived pain for the temporal heat stimulation of the QST-TTS (Co-VAS) at these time-points. On these days of pain testing, except for Day 15, participants will also complete a cannabis rating form and subjective effects visual analog scales pre-cannabis administration (0945h), for a full-time course after the first cannabis administration (1015h, 1045h, 1115h, 1145h, 1215h), and after each subsequent cannabis administration timepoint (1315h, 1615h). On Day 15, these assessments will conclude with the 1215 time-point. Vital signs will be taken before and after each pain assessment. In addition, vital signs will be taken halfway through the duration of each CPT assessment. If vital sign parameters are exceeded at any point during the CPT task, staff will follow the same assessment procedures as stated in the training section above.

On days when there are no pain assessments, participants will complete just the cannabis rating form and subjective effects battery at 1015h, 1315h, and 1615h.

Cannabis Administration

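### Questions 2 and 3 compare post-smoking pain between days without saying how the same-day pre-dose test enters, so changed analgesia and changed resting pain are mixed; the QST-TTS direction also conflicts with the rest of the protocol

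*Protocol*

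**What the plan says.** The protocol's General Overview gives the pain criteria. Question 2 requires "a significant decrease in CPT latencies and QST-TTS response following active cannabis administration on Day 12 or Day 15 compared to Day 9". Question 3 is "defined as a significant increase in CPT latencies and QST-TTS response" (and in the good-drug-effect rating) "after active cannabis administration when Day 9 of the Active Phase is compared to Day 1". Neither criterion refers to the pre-dose value of the day.

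That value is collected. Under the heading CPT and QST-TTS, tests are scheduled "30 minutes before the 1000h cannabis administration (baseline), and 0, 15, 30, 45, 60, and 90 minutes post-cannabis administration" on Days 1, 2, 5, 8, 9, 12 and 15.

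The analysis text (protocol, Statistical/Data Analysis Plan; SAP, Overview) names a repeated measures ANOVA by cannabis condition and day, plus planned comparisons. The protocol says these are outlined below, but no list follows, and the SAP has none. No change score, covariate or time-within-day factor is named.

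The protocol expects resting pain to move. Aim 1 predicts that "abrupt abstinence will result in increased CPT and QST-TTS responses, indicative of withdrawal-induced hyperalgesia", and the statement of purpose says that "it is possible that abrupt cessation of cannabis use will lead to worsened baseline pain".

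On direction, Experimental Assessments says that "cannabis use may decrease QST-TTS response, mirroring analgesia on the CPT during active cannabis administration vs. placebo".

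**The concern.** A post-smoking score reflects both how sensitive the participant was that morning and what the cannabis then did. Comparing post-smoking scores between days isolates the second only if the first is stable. The protocol's own hypothesis is that it is not stable, and Day 9, which directly follows the inactive phase, is in both contrasts.

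The dosing history before the pre-dose test also differs sharply between days, since active-phase dosing is "at the same three time-points (1000, 1300, 1600), with the exception of Day 15 where they will be administered active cannabis only at 1000". Tolerance, or its absence, could therefore be reported when only resting pain had moved, which is the effect Aim 1 is meant to detect.

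The criteria also ask CPT latency and QST-TTS response to fall together (Question 2) or rise together (Question 3). A longer latency means less pain. A higher QST-TTS response means more pain. Under analgesia the two should move in opposite directions.

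**Working it through.** **The plan's own figure.** The sample-size justification gives alpha 0.05, d=0.7, correlation 0.6 and 20 completers, with no target power. The paired effect size is 0.7/sqrt(2(1-0.6)) = 0.7/0.894 = 0.783, and the noncentral t gives 91% power at n=20. At the N=16 given in the General Overview it is 83%. Dropout agrees: 24 - 4 = 20.

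**Decomposition.** Let R be the resting level and A the acute effect on a given day, and assume that they add. Then:

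post-dose contrast (Day 12 - Day 9) = [A12 - A9] + [R12 - R9]

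The same holds for Day 15 against Day 9 and for Day 9 against Day 1.

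**Timing of the 0930h test.**
- Day 9: last active dose at 1600h on Day 1, so 8 x 24 - 6.5 = 185.5 h.
- Days 12 and 15: last active dose at 1600h the day before, so 17.5 h.

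**Direction for CPT latency.** If Aim 1 is right, R9 is low. Recovery by Day 12 or 15 then raises latency and hides a loss of analgesia. A low R9 likewise hides restored analgesia on Day 9 against Day 1. A resting shift the other way mimics either finding.

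**Size (illustration only).** The documents give no shift sizes, so those below are assumed. Settings: one outcome, one post-dose time-point, one day pair, n=20, two-sided 0.05, counting only significant results in the stated direction. The SD of the difference is sqrt(2(1-r)) = 0.894 at r=0.6.

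| Resting shift | Power for a true 0.7 SD change, shift opposing | Significant result with no change in analgesia |
|---|---|---|
| 0 | 91% (0.7/0.894 = 0.783) | 2.5% |
| 0.2 SD | 66% (0.5/0.894 = 0.559) | 16% (0.2/0.894 = 0.224) |
| 0.35 SD | 38% (0.35/0.894 = 0.391) | 38% |
| 0.7 SD | 2.5% | 91% |

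**Sensitivity.**
- *Day 12 or Day 15.* Counting either day as meeting the criterion (simulated, r=0.6 between all days), power at 0.35 SD is about 55%. False results at 0.2 and 0.35 SD are about 25% and 55%.
- *Higher correlation.* The protocol quotes 0.60-0.95. For one day pair at 0.35 SD, r=0.8 gives 0.35/0.632 = 0.553 and r=0.9 gives 0.35/0.447 = 0.783. Power is 65% and 91%; false results are also 65% and 91%.
- *Mean of six post-dose tests.* With between-day r=0.6 and same-day correlation w, the SD is sqrt(2[(w-0.6) + (1-w)/6]) = 0.365, 0.548, 0.683 for w = 0.6, 0.7, 0.8. Power at 0.35 SD is 98%, 77%, 58%, but the estimate is still halved. False results at that shift are also 98%, 77%, 58%.

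**QST-TTS taken literally.** Loss of analgesia raises the response, so it cannot produce the required decrease: for a true 0.7 SD loss at n=20, r=0.6, the probability is about 6e-8. Recovery from Day 9 hyperalgesia of 0.2, 0.35 or 0.7 SD lowers the response and meets the criterion in 16%, 38% and 91%.

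**The case against.** **Silence is not exclusion.** A reader might infer that the plan leaves out the pre-dose test. The documents do not say so: the test is labelled as baseline, planned comparisons are mentioned without being listed, and Figure 1, which is not shown, is said to illustrate all three questions and may add detail. This stands, and the point is limited to use that is not specified. The written criterion is still a post-dose comparison.

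**The post-dose contrast is not shown to be wrong.** A reader might infer that change from pre-dose is the right measure. That does not follow. If smoking fully relieves Day 9 hyperalgesia of 0.35 or 0.7 SD and analgesia does not change, the change contrast is falsely positive in 22-38% or 65-91% (one time-point, n=20, w 0.6-0.8). Which contrast is right depends on additivity, which the documents do not settle. This stands and shapes the fix.

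**The percentages are fragile.** The protocol describes its correlations as between active and inactive conditions and does not tie d=0.7 to a day-to-day change in analgesia. All shift sizes are assumed. If both outcomes must meet the criterion as written, a resting shift moves them in opposite directions and the per-outcome figures do not apply. This stands. The figures illustrate a mechanism and do not predict the trial's error rate.

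**The QST-TTS wording may be a slip.** Aim 1 also uses response loosely for the CPT. This is plausible, and the matter is separate from pre-dose adjustment. It still needs correcting, because the criterion decides what counts as a finding.

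**Conclusion.** The concern holds in a limited form. As written, the contrasts for Questions 2 and 3 mix changed analgesia with the resting-pain change that Aim 1 predicts, and the use of the same-day pre-dose test is unspecified. Under the planning values, an assumed opposing shift of 0.35 SD takes power for one outcome and one day pair from 91% to 38%. The same shift alone gives a significant result in 38%. With either day allowed, both figures are about 55%. This rests on additivity, the assumed shifts, and d=0.7 applying to this contrast.

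The QST-TTS criterion conflicts with Aim 1 and the assessment description whatever the shift sizes.

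Two stronger readings are not supported. A reader might infer that the study cannot examine resting pain at all, but pre-dose scores are scheduled on Days 1, 9, 12 and 15. A reader might also infer that Question 1 has no baseline, but the pre-dose test carries that label; only its reference day is absent from the available text, and Figure 1 may give it.

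This should be changed before results are reported. For a study that calls itself a pilot, it is not grounds for rejecting the design.

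**What to change.** For Questions 2 and 3, add time-point (-30 min against the mean of the six post-dose tests) as a within-subject factor. For Day 9 against Day 1, and for Days 12 and 15 against Day 9, report with 95% CIs:

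1. the post-dose contrast;
2. the day-by-time-point contrast, that is, change from same-day pre-dose;
3. the between-day contrast of -30 min scores, which equals (1) minus (2).

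Optionally add the post-dose contrast adjusted for the pre-dose value as a sensitivity analysis. Interpret a post-dose difference as changed analgesia only in light of (3) and its CI, and state when the two explanations cannot be separated. Correct the QST-TTS direction in the General Overview to agree with Aim 1 and Experimental Assessments. The protocol says the study is in data analysis only, so date the change and label it as made after data collection.

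**Cost.** No new data are needed. The change contrast has SD sqrt(2(1-w)(1+1/k)) for k post-dose tests averaged. At n=20 and w = 0.6-0.8, its power for 0.7 SD is 65-91% with one post-dose test and 87-99% with six. It also has the bias described above, so it is reported beside the post-dose contrast and does not replace it. The -30 min contrast is imprecise: its 95% CI half-width at n=20 is 2.093 x 0.894/sqrt(20) = 0.42 SD. A non-significant result there does not show that resting pain was stable.
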